7.1.5.2. Incomplete Dates

If the onset date of the AE is incomplete and the AE stop date is not prior to the first dosing date of study drug, then the month and year (or year alone if month is not recorded) of onset determine whether an AE is treatment-emergent. The event is considered treatment-emergent if both of the following 2 criteria are met:

- The AE onset is the same as or after the month and year (or year) of the first dosing date of study drug, and
- The AE onset date is the same as or before the month and year (or year) of the date corresponding to 30 days after the date of the last dose of study drug

An AE with completely missing onset and stop dates, or with the onset date missing and a stop date later than the first dosing date of study drug, will be considered to be treatment-emergent. In addition, an AE with the onset date missing and incomplete stop date with the same or later month and year (or year alone if month is not recorded) as the first dosing date of study drug will be considered treatment-emergent.

7.1.6. Summaries of Adverse Events and Deaths

Treatment-emergent (TE) AEs will be summarized based on the Safety Analysis Set for the BD Phase, and the LT analysis. TEAEs in the OLE Phase will be summarized based on the OLE Analysis Set. In LT analysis, TEAEs will be those included in BD Phase/OLE Phase summary.

The number and percentage of subjects who experienced at least 1 TEAE will be provided and summarized by SOC, PT, and treatment group. For other AEs described below, summaries will be provided by SOC, PT, and treatment group:

- TEAEs of Grade 3 or higher
- TEAEs by severity
- All TE treatment-related AEs
- TE Treatment-related AEs of Grade 3 or higher
- TE Treatment-related AEs by severity
- All TE SAEs
- All TE treatment-related SAEs
- All TEAEs leading to premature discontinuation of study drug
- All TEAEs leading to death (ie, outcome of death)

- All TEAEs leading to dose interruption of study drug
- All TEAEs leading to dose reduction of study drug (OLE Phase only)
- All AEs recorded between screening and prior to first dose of study drug

A brief, high-level summary of TEAEs, TEAEs with Grade 3 or Higher, TEAEs Related to Study Drug, TEAEs Related to Study Drug with Grade 3 or Higher, TE Serious AEs, TE Serious AEs Related to Study Drug, and TEAEs Leading to Premature Discontinuation of Study Drug will be provided by treatment group and by the number and percentage of subjects who experienced the above AEs. All deaths observed in the study will be also included in this summary.

Multiple events will be counted only once per subject in each summary. Adverse events will be summarized and listed first in alphabetic order of SOC, and then by PT in descending order of frequency of BD GS-9674 100 mg group within each SOC in the BD Phase/ total frequency within each SOC for the OLE Phase/ frequency of LT GS-9674 initially in 100 mg group in the long-term summary. For summaries by severity grade, the most severe grade will be used for those AEs that occurred more than once in an individual subject during the study.

In addition to the above summary tables, the following tables will be summarized by PT only, in descending order of frequency in the GS-9674 100 mg group in the BD Phase/ total frequency for the OLE Phase/ frequency of LT GS-9674 initially in 100 mg group in the long-term summary:

- All TEAEs
- TEAEs of Grade 3 or higher
- TE treatment-related AEs
- TE treatment-related AEs of Grade 3 or higher
- All TE SAEs
- All TE treatment-related SAEs
- In addition, data listings will be provided for the following:
 - All AEs, indicating whether the event is treatment-emergent
 - All AEs of Grade 3 or higher
 - SAEs
 - All TEAEs leading to Death

- AEs leading to premature discontinuation of study drug
- AEs leading to dose interruption of study drug
- AEs leading to dose reduction of study drug (OLE Phase only)

7.2. **Laboratory Evaluations**

Laboratory data collected during the study will be analyzed and summarized using both quantitative and qualitative methods. Summaries of laboratory data will be provided for the Safety Analysis Set/OLE Analysis Set and will include data collected up to the last dose of study drug plus 30 days in the BD Phase (and on or before the first dose date in the OLE Phase)/OLE Phase for subjects who have permanently discontinued study drug, or all available data at the time of the database snapshot for subjects who were ongoing at the time of an interim analysis. Data obtained at the ET or FU visit will be included in the by-visit summaries by their nominal visit ID in BD/OLE Phase, regardless of the relevant number of days to the last dose date. LT analysis will include data summarized in BD Phase/OLE Phase. Data obtained after the last dose of study drug plus 30 days in the BD (and prior to first dose date of OLE Phase)/OLE Phase will not be included in the evaluation of the TE laboratory abnormalities in the LT analysis. The analysis will be based on values reported in conventional units. When values are below the LOQ, they will be listed as such, and the closest imputed value will be used for the purpose of calculating summary statistics as specified in Section 3.7.

A by-subject listing for laboratory test results will be provided by subject ID number and visit in chronological order for hematology, serum chemistry, and urinalysis separately. Values falling outside of the relevant reference range and/or having a severity grade of 1 or higher on the CTCAE severity grade will be flagged in the data listings, as appropriate.

No formal statistical testing is planned.

7.2.1. **Summaries of Numeric Laboratory Results**

Descriptive statistics will be provided by treatment group for HOMA-IR, HbA1c, albumin, creatinine, fasting insulin, fasting glucose, prothrombin time, INR, WBC, neutrophils, lymphocytes, hemoglobin, platelets as follows:

- Baseline values
- Values at each postbaseline visit
- Change from baseline at each postbaseline visit

in the BD Phase, the OLE Phase and the LT analysis, separately.

A baseline laboratory value will be defined as the last measurement obtained on or prior to the date/time of first dose of study drug. Change from baseline to a postbaseline visit will be defined as the visit value minus the baseline value. The mean, median, Q1, Q3, minimum, and maximum

values will be displayed to the reported number of digits; SD values will be displayed to the reported number of digits plus 1.

Median (Q1, Q3) of the observed values for HOMA-IR, HbA1c, albumin, creatinine, fasting insulin, fasting glucose, prothrombin time, INR, WBC, neutrophils, lymphocytes, hemoglobin, platelets will be plotted using a line plot by treatment group and visit.

In the case of multiple values in an analysis window, data will be selected for analysis as described in Section 3.8.3.

7.2.2. **Graded Laboratory Values**

The CTCAE Version 4.03 will be used for assigning toxicity grades (0 to 4) to laboratory results for analysis. Grade 0 includes all values that do not meet the criteria for an abnormality of at least Grade 1. For laboratory tests with criteria for both increased and decreased levels, analyses for each direction (ie, increased, decreased) will be presented separately.

For the baseline ALP, ALT, AST, total bilirubin toxicity grades at the BD Phase, the CTCAE version 4.03 will be used to assign grades to the derived average values. See [Appendix 2](#) for the link to CTCAE 4.03.

7.2.2.1. **Treatment-Emergent Laboratory Abnormalities**

Treatment-emergent laboratory abnormalities are defined as values that increase at least 1 toxicity grade from baseline at any postbaseline time point, up to and including the date of last dose of study drug plus 30 days in the BD Phase (and on or before the first dose of the OLE Phase)/OLE Phase for subjects who permanently discontinued study drug, or the last available date in the database snapshot for subjects who were still on treatment at the time of an interim analysis. LT analysis will include data summarized in BD Phase/OLE Phase. Data obtained after the last dose of study drug plus 30 days in the BD (and prior to first dose date of OLE Phase)/OLE Phase will not be included in the evaluation of the TE laboratory abnormalities in the LT analysis. If the relevant baseline laboratory value is missing, any abnormality of at least Grade 1 observed within the time frame specified above will be considered treatment-emergent.

7.2.2.2. **Treatment-Emergent Marked Laboratory Abnormalities**

Treatment-emergent marked laboratory abnormalities are defined as values that increase from baseline by at least 3 toxicity grades at any postbaseline time point, up to and including the date of the last dose of study drug plus 30 days in BD Phase (and on or before the first dose of OLE Phase)/OLE Phase for subjects who permanently discontinued study drug or the last available date in the database snapshot for subjects who were still on treatment at the time of an interim analysis. LT analysis will include data summarized in BD Phase/OLE Phase. Data obtained after the last dose of study drug plus 30 days in the BD (and prior to first dose date of OLE Phase)/OLE Phase will not be included in the evaluation of the TE laboratory abnormalities in the LT analysis. If the relevant baseline laboratory value is missing, any Grade 3 or 4 values observed within the timeframe specified above will be considered treatment-emergent marked abnormalities.

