1.2. Study Design

This is a Phase 2 randomized, double-blind, placebo-controlled study evaluating the safety, tolerability, and efficacy of GS-9674 in subjects with PSC without cirrhosis.

[figure not shown]
The study consists of 2 phases, a BD Phase and an OLE Phase.

BD Phase: Includes a 4-week screening period, 12 weeks of blinded treatment, and a BD Phase follow-up visit 4 weeks after completion of blinded treatment.

Subjects completing the Blinded Study Phase without permanently discontinuing study drug will be eligible to participate in the OLE Phase of the study. OLE Phase: Includes a 96-week OLE treatment and an OLE Phase follow-up visit 4 weeks after completion of open label treatment.

The overall study design is presented graphically in [Figure 1-1](#).

Figure 1-1. Overall Study Design

Eligible subjects are randomly assigned to 1 of the following 3 treatment groups in a 2:2:1 ratio:

- GS-9674 30 mg + PTM GS-9674 100 mg orally once daily (n = 20);
- GS-9674 100 mg + PTM GS-9674 30 mg orally once daily (n = 20);
- PTM GS-9674 30 mg + PTM GS-9674 100 mg orally once daily (n = 10).

where PTM stands for Placebo to Match.

Central randomization is used. The randomization schedule is stratified by the presence or absence of ursodeoxycholic acid (UDCA) use.

Study drugs are administered for a total of 12 weeks from the Baseline/Day 1 visit during the BD Phase and 96 weeks during the OLE Phase. During the OLE Phase, subjects begin with open label treatment of GS-9674 (100 mg once daily). The dose of GS-9674 may be reduced from 100 mg to 30 mg (or subsequently increased back to 100 mg) at the principal investigator's (PI) discretion with the approval of the medical monitor, as required.

Subjects will be unblinded to their BD Phase treatment assignment after the primary analysis has been completed, approximately 6 weeks after all subjects have completed the BD Phase or early terminated. The schedule of assessments is provided as an appendix to this analysis plan ([Appendix 1](#)).

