7.1.5. Treatment-Emergent Adverse Events

7.1.5.1. Definition of Treatment-Emergent Adverse Events

Treatment-emergent adverse events (TEAEs) are defined as 1 or both of the following:

- Any AEs with an onset date on or after the study drug start date and no later than 30 days after permanent discontinuation of study drug in the BD Phase (and before the first dosing date in the OLE Phase)/OLE Phase.
- Any AEs leading to premature discontinuation of study drug in the BD/OLE phase.

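### An AE that begins before the first OLE dose and leads to a dose reduction or interruption in the OLE is missing from the OLE table of that action, because TEAE phase follows onset date

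*SAP*

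**What the plan says.** **Definition (SAP 7.1.5.1).** The first route to being treatment-emergent is by date: "Any AEs with an onset date on or after the study drug start date", up to 30 days after "permanent discontinuation of study drug in the BD Phase (and before the first dosing date in the OLE Phase)/OLE Phase". The BD window therefore closes before the first OLE dose, and the OLE window opens with it. The second route is by action: "Any AEs leading to premature discontinuation of study drug in the BD/OLE phase". Interruption and reduction have no such route.

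**Tables (SAP 7.1.6).** Two of the planned summaries are "All TEAEs leading to dose interruption of study drug" and "All TEAEs leading to dose reduction of study drug (OLE Phase only"). Both are restricted to TEAEs. Neither says in which phase the action must have occurred, apart from the OLE label on the reduction table. For the long-term analysis, "In LT analysis, TEAEs will be those included in BD Phase/OLE Phase summary".

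**Listings (SAP 7.1.6).** The by-subject listings cover AEs, not only TEAEs. They include "AEs leading to dose reduction of study drug (OLE Phase only") and a matching listing for interruption.

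**Design (SAP 1.2).** All OLE subjects begin on open-label 100 mg, and "The dose of GS-9674 may be reduced from 100 mg to 30 mg" and later raised again. Only subjects who complete the BD Phase without permanently discontinuing drug may enter the OLE.

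**Grouping (SAP 3.2).** BD analyses summarize BD Phase data only, and OLE analyses summarize OLE Phase data only.

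**The concern.** Safety and tolerability are the trial's primary objective (SAP 1.1). AEs that cause drug to be stopped, interrupted or reduced are among the most direct tolerability measures. An action belongs to the treatment the subject was on when it was taken, but the SAP selects events for the reduction and interruption tables by when the AE began. The two can fall in different phases. A subject may carry an unresolved AE from the BD Phase, or from the weeks off drug before OLE Day 1, into open-label 100 mg, and that AE may then prompt a dose change. With the planned sizes, up to 20 + 10 = 30 of 50 subjects would come to 100 mg from 30 mg or placebo, so the tables ought to handle this case. The OLE tables would understate AE-driven reductions and interruptions. It is also unclear where an interruption or stop in the OLE would appear on the BD side.

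**Working it through.** The plan gives no figure to reproduce. The check traces one AE through the definition and the tables.

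**Case.** The AE begins on or after the first BD dose and before the first OLE dose, is ongoing at OLE Day 1, remains one AE record, and leads to an action during the OLE.

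**Step 1: which phase's TEAE is it?** By the date route its onset precedes the OLE window, so it is not an OLE TEAE. It is a BD TEAE if onset falls within 30 days of the last BD dose. By the action route it becomes an OLE TEAE only if the action is premature discontinuation.

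**Step 2: where does it appear?**

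| Action in the OLE | OLE table of that action | BD table of that action | Listing of that action |
|---|---|---|---|
| Reduction | Absent: not an OLE TEAE | No such table | Present |
| Interruption | Absent: not an OLE TEAE | Not settled | Present |
| Discontinuation | Present, by the action route | Not settled | Present |

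**Step 3: why the BD column is not settled.** For interruption and discontinuation, 7.1.6 asks only that the AE be a TEAE and that it led to the action. Read literally, a BD TEAE that led to an OLE action satisfies both conditions and enters the BD table. If the BD-data-only rule in 3.2 is applied to the action as well as to the AE, the OLE action does not count and the AE stays out. The SAP does not choose between the two. Under the second reading, the interruption is in neither phase's table.

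**Step 4: size per subject.** Planned sizes in SAP 1.2 are 20, 20 and 10, so the OLE Total column holds at most 50.

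- OLE Total: 1/50 = 2 percentage points, and more if fewer than 50 enter.
- OLE columns by previous treatment: at least 1/20 = 5 points for a former GS-9674 arm and at least 1/10 = 10 points for former placebo.
- BD table, only under the literal reading of 7.1.6: 1/20 = 5 points in a GS-9674 arm and 1/10 = 10 points in placebo.

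These are sizes per event. The document gives no basis for estimating how many such events will occur.

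**The case against.** **Onset-based assignment is conventional, and the study is descriptive.** True: no test, interval or sample size depends on it. But the SAP already departs from onset for discontinuation, and it gives no reason for treating the other two actions differently.

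**The events are not lost.** This stands. The listings of AEs leading to reduction and to interruption are not restricted to TEAEs, so the case appears there, and in a study of about 50 subjects a listing can be read case by case. The error is in the tabulated counts, not in the report as a whole.

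**The case is narrow.** The AE must still be ongoing at the first OLE dose, which normally follows about four weeks off drug, and must stay one record. An AE that resolves and recurs, or whose worsening is entered as a new record, has an OLE onset and is tabulated correctly. Those recording rules may sit in the protocol or CRF instructions, which are not at hand; this SAP does not state them. This limits the frequency but does not correct the rule.

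**Stronger readings that the document does not support.**

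- A reader might infer that an OLE interruption or stop is counted against the blinded arm, that the BD discontinuation table will contradict the disposition table, or that BD tables will change between the primary and final analyses. Each needs 7.1.6 read without 3.2. The placement is unspecified, not wrong by a stated rule.
- A reader might infer that the reduction appears in no table at all. The OLE-only label may bar a long-term reduction table, or may simply say where reductions can occur; if so, a long-term table could show the event. Such a table would still omit subjects who began on placebo, since the long-term groups in 3.2 include only those who began on 100 mg or 30 mg.

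**Conclusion.** The point holds in a limited form. Under 7.1.5.1 and 7.1.6 as written, an AE with onset before the first OLE dose that leads to an OLE reduction or interruption is left out of the OLE table for that action. This follows from stated rules and makes the count for a tolerability measure wrong. Each affected subject is worth at least 2 points of OLE Total.

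Separately, the SAP does not say whether a BD table of AEs leading to interruption or discontinuation may include an action taken in the OLE. That is an ambiguity to close, not a demonstrated miscount.

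The conclusion assumes that the AE is kept as a single record across the off-drug gap and that the planned sizes are not exceeded. It concerns descriptive tables only, but these serve the primary objective, so the text should be corrected.

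**What to change.** Leave the TEAE definition in 7.1.5.1 unchanged. Extending its second bullet to interruption and reduction would bring BD-onset AEs into every OLE TEAE table, and would make AEs with onset before first dosing treatment-emergent whenever they led to a BD interruption.

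In 7.1.6, state that:

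- the tables of AEs leading to discontinuation, interruption and reduction are assigned to the phase in which the action was taken, determined from study drug administration dates;
- for interruption and reduction this applies whatever the AE onset date within the study treatment period, meaning on or after the first BD dose, while discontinuation keeps the action rule it already has in 7.1.5.1;
- an action taken in the OLE is not counted in a BD table.

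The cost is a few lines of SAP text and a date merge with study drug administration records, which SAP 4.2.2.2 already plans to list. The one downside is that a BD-onset AE can appear in an OLE table of AEs leading to an action without appearing in the OLE table of all TEAEs. A footnote to the affected tables should say so.

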7.2.2.3. Summaries of Laboratory Abnormalities

The following summaries (number and percentage of subjects) for treatment-emergent laboratory abnormalities will be provided by lab test and treatment group for the BD Phase, the OLE Phase, and the LT analysis, separately; subjects will be categorized according to the most severe postbaseline abnormality grade for a given lab test:

- Graded laboratory abnormalities
- Grade 3 or 4 laboratory abnormalities
- Marked laboratory abnormalities

For all summaries of laboratory abnormalities, the denominator is the number of subjects with nonmissing postbaseline values up to 30 days after last dose date in the study phase reported. LT analysis will include data summarized in BD Phase/OLE Phase. Data obtained after the last dose of study drug plus 30 days in the BD (and prior to first dose date of OLE Phase)/OLE Phase will not be included in the evaluation of the TE laboratory abnormalities in the LT analysis.

A by-subject listing of treatment-emergent Grade 3 or 4 laboratory abnormalities will be provided by subject ID number and visit in chronological order. This listing will include all test results that were collected throughout the study for the lab test of interest, with all applicable severity grades or abnormal flags displayed.

7.2.3. Liver-related Laboratory Evaluations

Liver-related abnormalities after initial study drug dosing will be examined and summarized using the number and percentage of subjects who were reported to have the following laboratory test values for postbaseline measurements.

Subjects meet criteria for liver-related events:

- For subjects with normal baseline ALT (AST):
 - ALT (AST) $> 3 \times$ ULN
 - Total bilirubin $> 2 \times$ ULN
 - INR > 1.5 (except for subjects on anticoagulant therapy)
- For subjects with elevated ALT (AST) (\geq upper limit of normal [ULN]) at study start:
 - ALT (AST) $> 2 \times$ baseline
 - Total bilirubin $> 2 \times$ ULN
 - INR > 1.5 (except for subjects on anticoagulant therapy)

Subjects meet criteria for drug withheld:

- ALT (AST) $> 5 \times$ baseline
- ALT (AST) $> 10 \times$ ULN
- ALT (AST) $> 3 \times$ baseline with total bilirubin $> 2 \times$ ULN
- ALT (AST) $> 3 \times$ baseline with total bilirubin $> 1.5 \times$ baseline
- ALT (AST) $> 3 \times$ baseline with INR > 1.5 (except for subjects on anticoagulant therapy)
- ALT (AST) $>$ baseline with total bilirubin $> 2 \times$ ULN, and INR > 1.5 (except for subjects on anticoagulant therapy)
- ALT (AST) $>$ baseline with total bilirubin $> 1.5 \times$ baseline, and INR > 1.5 (except for subjects on anticoagulant therapy)

The summary will include data from all postbaseline visits up to 30 days after the last dose of study drug in the BD Phase (and on or before the first dose of the OLE Phase)/OLE Phase. LT analysis will include data summarized in BD Phase/OLE Phase. Data obtained after the last dose of study drug plus 30 days in the BD (and prior to first dose date of OLE Phase)/OLE Phase will not be included in the evaluation of the TE laboratory abnormalities in the LT analysis. For individual laboratory tests, subjects will be counted once based on the most severe postbaseline values. For the criteria of ALT (AST) and total bilirubin, INR, subjects will be counted once when the criteria are met at the same postbaseline visit date. The denominator is the number of subjects in the Safety Analysis Set/OLE Analysis Set who have nonmissing postbaseline values of all relevant tests at the same postbaseline visit date in the corresponding baseline group. A listing of subjects who met at least 1 of the above criteria will be provided.

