5.2. Baseline Characteristics

Other baseline characteristics include:

- Body weight
- Height
- Body mass index (BMI) as a continuous variable and by categories ($< 18.5 \text{ kg/m}^2$, $18.5 \text{ to } < 25 \text{ kg/m}^2$, $25 \text{ to } < 30 \text{ kg/m}^2$ and $\geq 30 \text{ kg/m}^2$)
- UDCA use (Yes or No, based on concomitant medication page)
- ALP as a continuous variable
- Total bilirubin as a continuous variable and by categories ($\leq \text{ULN}$ or $> \text{ULN}$)
- Direct bilirubin
- ALT as a continuous variable and by categories ($< \text{ULN}$ and $\geq \text{ULN}$)
- AST as a continuous variable and by categories ($< \text{ULN}$ and $\geq \text{ULN}$)
- GGT
- Fasting serum glucose
- Fasting insulin
- Homeostatic assessment of insulin resistance (HOMA-IR)
- Hemoglobin A1c (HbA1c)
- Fasting triglycerides

- Total cholesterol
- High density lipoprotein-cholesterol (HDL-C)
- Calculated fasting low density lipoprotein-cholesterol (LDL-C)
- Calculated fasting very low density lipoprotein-cholesterol (VLDL-C)
- Calculated fasting non high density lipoprotein-cholesterol (Non-HDL-C)
- ELF™ score and components (hyaluronic acid [HA], procollagen III amino terminal peptide [PIIINP], tissue inhibitor of metalloproteinase 1 [TIMP-1])
- FibroSURE/FibroTest® and selected components (α_2 -macroglobulin, haptoglobin, apolipoprotein A1)
- FibroScan®
- hsCRP
- Fasting total bile acids
- Albumin
- INR
- Platelets
- Creatinine
- Smoking status at baseline
- Diabetes mellitus diagnosis at baseline (yes or no, based on medical history page)
- Taking hypertension treatment at baseline (yes or no, based on prior and concomitant medication page)
- Inflammatory bowel disease (IBD) history (yes or no, based on medical history page)
- Baseline partial Mayo score for patients with IBD history
- Baseline classification of biliary tree disease due to PSC based on MRCP

These baseline characteristics will be summarized by treatment groups 1 – 4 and overall (Section 3.2) using descriptive statistics for continuous variables and using number and percentage of subjects for categorical variables. The summary of baseline characteristics will be provided for the Safety Analysis Set. In addition, baseline characteristics will be summarized by baseline UDCA use in a separate table. No formal statistical testing is planned.

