Appendix 3. Programming Specifications

FibroSURE/FibroTest® Calculation:

Step-1 formula	$f5 = 4.467 \times \text{Log}[\alpha_2\text{-macroglobulin(g/L)}] - 1.357 \times \text{Log}[\text{Haptoglobin (g/L)}] + 1.017 \times \text{Log}[\text{GGT(U/L)}] + 0.028 \times [\text{Age (year)}] + 1.737 \times \text{Log} [\text{Total Bilirubin (umol/L)}] - 1.184 \times [\text{ApoA1 (g/L)}] + 0.301 \times \text{Sex (female = 0, male = 1)} - 5.540$
Step-2 formula	$\text{FibroSURE/FibroTest}^{\circledR} \text{ Score} = 1/(1+\text{exp}^{(-f5)})$
Note	
• In the formula, SI value and units should be applied.• The Log function in the formula is with base 10.• FibroSURE/FibroTest® score should be calculated from the parameters from the same blood draw• Age is when the blood draw was taken

For subject with Gilbert's syndrome or hemolysis according to the medical history page at screening, the FibroSURE/FibroTest® score will be calculated using Direct Bilirubin instead of Total Bilirubin in above formula throughout the study.

HOMA-IR Calculation:

HOMA-IR = fasting glucose (mg/dL) \times fasting insulin (muIU/mL) / 405. Keep 2 decimal places. The lab parameters need to be measured from the same blood draw.

Pooled Cohort Risk Score:

No.	Parameters	Coefficient			
		Female		Male	
		White or Other	African America	White or Other	African America
1	ln Age (y)	-29.799	17.114	12.344	2.469
2	ln Age, Squared	4.884	N/A	N/A	N/A
3	ln Total Cholesterol (mg/dL)	13.540	0.940	11.853	0.302
4	ln Age × ln Total Cholesterol	-3.114	N/A	-2.664	N/A
5	ln HDL-C (mg/dL)	-13.578	-18.920	-7.990	-0.307
6	ln Age × ln HDL-C	3.149	4.475	1.769	N/A
7	ln Treated Systolic BP (mm Hg)	2.019	29.291	1.797	1.916
8	ln Age × ln Treated Systolic BP	N/A	-6.432	N/A	N/A
9	ln Untreated Systolic BP (mm Hg)	1.957	27.820	1.764	1.809
10	ln Age × ln Untreated Systolic BP	N/A	-6.087	N/A	N/A
11	Current Smoker (1=Yes, 0=No)	7.574	0.691	7.837	0.549
12	ln Age × Current Smoker	-1.665	N/A	-1.795	N/A
13	Diabetes (1=Yes, 0=No)	0.661	0.874	0.658	0.645
A	Baseline Survival	0.9665	0.9533	0.9144	0.8954
B	Individual Sum = $\sum(\text{coefficient} * \text{parameter})$	For each individual patient, individual sum is summation of product of each parameter and its corresponding coefficient for that sex-race group for all parameters listed above (#1 -#13). Note: N/A indicates that the specific coefficient is not available thus the corresponding parameter will not be included in calculation.			

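### The single-test total bilirubin row in SAP Section 7.2.3 is grouped by baseline ALT (AST) and ignores baseline bilirubin, so a subject already above 2 x ULN who does not change is counted as a liver-related event

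*SAP*

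**What the plan says.** SAP Section 7.2.3 counts subjects meeting liver-related laboratory criteria at postbaseline visits. The event rows come in two groups: "For subjects with normal baseline ALT (AST") and "For subjects with elevated ALT (AST") at or above ULN at study start.

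- **ALT (AST).** The criterion changes with the group: > 3 x ULN if baseline is normal, > 2 x baseline if elevated.
- **Total bilirubin.** The criterion is "Total bilirubin $> 2 \times$ ULN" in both groups.
- **INR.** The criterion is the same in both groups but carries an exception: "INR > 1.5 (except for subjects on anticoagulant therapy").

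The counting rule is: "For individual laboratory tests, subjects will be counted once based on the most severe postbaseline values". Denominators are taken within the corresponding baseline group. The table is produced for the BD Phase, the OLE Phase and the LT analysis.

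A comparison of bilirubin with its own baseline does occur in the section, but only inside combined drug-withheld criteria ("with total bilirubin $> 1.5 \times$ baseline").

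Elsewhere, Section 5.2 summarises "Total bilirubin as a continuous variable and by categories", the categories being at or below ULN and above ULN. For subjects with Gilbert's syndrome or hemolysis in the medical history, Appendix 3 says that the FibroSURE/FibroTest "score will be calculated using Direct Bilirubin instead of Total Bilirubin in above formula throughout the study". Section 7.2.3 makes no mention of either condition.

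**The concern.** The ALT (AST) grouping keeps a pre-existing ALT or AST elevation from being read as a new event. Bilirubin sits inside that grouping but gets no such protection, because its criterion is the same on both sides and looks only at the postbaseline value. A bilirubin that was above the threshold before the first dose of the phase, and has not moved, therefore enters the table as a liver-related event.

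Safety and tolerability is the primary objective (Section 1.1), and the planned arms are 20, 20 and 10 (Section 1.2), so one subject visibly changes a row. In the BD Phase the placebo column gives some reference. In the OLE Phase (groups 5 to 8 of Section 3.2) and the LT analysis (groups 9 and 10) there is no placebo column against which to judge the count.

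**Working it through.** The SAP gives no figure for this point that could be reproduced. The check is a reading of the rule, followed by an illustration of its size.

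**1. The rule within Section 7.2.3**

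| Test | Normal baseline ALT (AST) | Elevated baseline ALT (AST) | Allowance for baseline or a non-drug cause |
|---|---|---|---|
| ALT (AST) | > 3 x ULN | > 2 x baseline | yes, through the grouping |
| Total bilirubin | > 2 x ULN | > 2 x ULN | none |
| INR | > 1.5 | > 1.5 | anticoagulant users excepted |

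Bilirubin is the only one of the three with no allowance.

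**2. A subject who does not change**

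Write the stable level as b x ULN. If b > 2, the first postbaseline value meets the row. If b is 2 or less and the value truly stays constant, the row is never met.

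**3. Ordinary visit-to-visit variation**

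Assume measured values are log-normal around a constant median b x ULN, independent between visits, with within-subject coefficient of variation CV. The SAP gives no CV, so 10%, 20% and 30% are assumptions. The BD Phase has k = 5 scheduled postbaseline visits on treatment (Weeks 1, 2, 4, 8, 12).

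P(counted) = 1 - Phi(ln(2/b)/s)^k, with s = sqrt(ln(1 + CV^2)).

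Example: b = 1.8 and CV = 20% give s = 0.198, ln(2/1.8)/s = 0.532, Phi = 0.7026, and P = 1 - 0.7026^5 = 0.83.

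| Stable level b (x ULN) | CV 10% | CV 20% | CV 30% |
|---|---|---|---|
| 1.0 | 0% | 0.1% | 4.5% |
| 1.2 | 0% | 2.5% | 19% |
| 1.5 | 1% | 32% | 59% |
| 1.8 | 54% | 83% | 89% |
| 2.2 | about 100% | 99.7% | 99.3% |

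A subject above the threshold is almost surely counted. A subject just below is counted often. Further down, the result depends strongly on the assumed CV.

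The OLE Phase has 12 scheduled postbaseline visits (Weeks 1, 2, 4, 8, 12, then every 12 weeks to 96). For b = 1.8 and CV = 10%, Phi = 0.8546 and P = 1 - 0.8546^12 = 0.85, against 0.54 with five visits.

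**4. Weight of one subject**

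- Whole arm: 1/20 = 5 points, 1/10 = 10 points.
- Within an ALT (AST) group the denominator is smaller. If an arm split evenly (an assumption), one subject would be 1/10 = 10 points in a dose arm and 1/5 = 20 points in placebo.

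**5. Chance that an arm contains such a subject**

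Let p be the proportion entering above 2 x ULN. It is not in the SAP and may be zero. P(at least one) = 1 - (1 - p)^n.

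| p (assumed) | Placebo, n = 10 | Dose arm, n = 20 |
|---|---|---|
| 0% | 0% | 0% |
| 2% | 18% | 33% |
| 5% | 40% | 64% |
| 10% | 65% | 88% |

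**6. OLE Phase**

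Section 1.2 makes subjects eligible for the OLE if they complete the blinded phase without permanently stopping study drug; it states no bilirubin condition. Under Section 3.8.3 the phase baseline is in general the last nonmissing value on or before the first dose of that phase. A subject above 2 x ULN on that value who remains there is counted as an OLE event.

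**The case against.** The case for leaving the table alone has several parts.

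- **Entry limits are unseen.** Protocol eligibility may exclude anyone near 2 x ULN, in which case the BD Phase count is unaffected. This stands. A reader might infer from Section 5.2 and Appendix 3 that such subjects are expected. They do not show that: one tabulates values above ULN, and the other is a conditional programming rule. The protocol may also restrict OLE entry in ways the SAP does not repeat.
- **Raised bilirubin in general is not counted.** A reader might infer that any elevation present before dosing becomes an event. It does not: a value that stays between 1 and 2 x ULN never meets the row.
- **The drug-withheld rows are not triggered.** A reader might infer that high baseline bilirubin also inflates those rows. Each row that uses bilirubin > 2 x ULN also requires ALT (AST) above baseline on the same visit date: either > 3 x baseline, or > baseline together with INR > 1.5. A subject who does not change meets none of them.
- **An absolute-threshold count is legitimate.** Section 7.2.3 does not call these rows drug-related, and the plan makes no formal tests. True, but the section already uses baseline for ALT (AST), and grouping bilirubin by another analyte serves neither purpose.
- **Other outputs help.** Treatment-emergent abnormalities in Section 7.2.2.1 require a rise of at least one grade from baseline. Section 7.2.3 also lists every subject meeting a criterion. These limit the harm considerably, but they do not correct the percentages in this table.

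**Conclusion.** The point holds in a limited form. The single-test bilirubin row is grouped by a variable that has no bearing on it and lacks the one that does. A subject above 2 x ULN at the baseline of the reporting phase is counted without any rise, and a subject just below may be counted by variation alone.

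The size in the BD Phase cannot be settled from the SAP. It ranges from nothing, if eligibility excludes such subjects, to 5 points per subject in a dose arm and 10 in placebo on whole-arm denominators, and more within an ALT (AST) group. The probabilities near the threshold rest on the assumed CV and on independence between visits. In the OLE Phase the gap is more exposed, since the SAP states no bilirubin condition for entry and there is no placebo reference.

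The documents do not support a claim that the planned arm comparison is biased, or that the table as a whole misstates liver injury. The point is minor: a cheap improvement in how one row reads.

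**What to change.** In Section 7.2.3:

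1. Take the total bilirubin row out of the ALT (AST) grouping.
2. Tabulate it by the subject's own baseline bilirubin in the reporting phase: baseline at or below 2 x ULN (new crossings) and baseline above 2 x ULN (shown separately, not dropped). Each denominator is the subjects in that baseline category with a postbaseline value. Use the baseline definitions of Section 3.8.3, and name the baseline that applies in the LT analysis.
3. In the listing of subjects meeting criteria, add baseline bilirubin and the Gilbert's syndrome or hemolysis status that Appendix 3 already needs.

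Thresholds and drug-withheld criteria stay unchanged.

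The cost is a sentence or two in the SAP and a few more rows with small cells, repeated for the BD, OLE and LT tables. Baseline bilirubin is already derived. Section 5.3 leaves general medical history uncoded, so the Gilbert's or hemolysis status has to be identified from the medical history page, which Appendix 3 requires in any case. One limit remains: a small move across the threshold, say from 1.95 to 2.05 x ULN, would still be a new crossing. That is why the listing should show the baseline value.
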